5.4. Study Blinding

The Sponsor or designee, the Investigator, study-site personnel, and the patient will be blinded to treatment assignment. The integrity of the clinical study will be maintained by observing the treatment blind. If knowledge of a patient's treatment assignment is required for the patient's clinical care and/or safety, the Investigator should consult with the Sponsor's medical monitor prior to breaking the blind.

5.4.1. Unblinding Treatment Assignment

Unblinding the treatment assignment of a patient may only be performed in emergencies where knowledge of the patient's treatment assignment is essential for management of the patient's medical care. Unblinding the treatment assignment by the investigator under any other circumstances will be considered a protocol violation. The investigator should make every effort to contact the Sponsor or designee prior to unblinding a patient's treatment assignment. In the event of any unblinding, emergency or accidental, the sponsor must be notified within 1 business day.

Unblinding will occur using the EDC system. The Investigator must record the date and time the blind was broken, the names of the personnel involved, and the reason that treatment assignment information was required. The date and time that the Sponsor or designee was notified will also be recorded.

5.5. Study Drug Administration

Study drug will be administered to all patients in the clinic by designated and trained site staff from Baseline to Week 14 (last injection prior to Maintenance Period).

5.5.1. Instructions for Administration in the Clinic

Syringes should be at room temperature prior to injection (refer to the applicable Instructions for Use provided by the sponsor).

5.5.2. Instructions for Administration at Home

During the Maintenance Period, patients or caregivers will be instructed to self-administer study drug during the Maintenance Period.

Study site staff will instruct the patient or their caregiver on the proper injection technique and the patient or their caregiver will demonstrate for site staff proper injection technique prior to beginning at-home administration. An instruction card with details of the injection procedures will be provided to the patient/caregiver to take home, and dosing compliance will be captured via an electronic diary.

Patients or caregivers who are not capable of administering study drug at home may continue to receive study drug injections in the clinic.

5.6. Study Drug Accountability

The Investigator must keep an accurate record of the number of cartons received, the study drug dispensed/used, and those returned to the Sponsor or designee. The Sponsor or designee will provide forms to facilitate inventory control. All study-drug accountability forms and treatment logs must be retained in the Investigator's permanent study file, and these records must be available for inspection at any time by the Sponsor, its designees, or by regulatory agencies.

The study monitor will perform drug accountability for all study drug at the site, and will assist in returning all used, unused, and expired study drug, to the Sponsor/designees, or destroy it according to the study site's standard operating procedure, if accepted by the Sponsor.

6. CONCOMITANT MEDICATIONS AND PROCEDURES

All medications (including over-the-counter drugs, vitamins, and antacids) and over-the-counter emollient(s) taken/used at screening and throughout the study must be recorded. Patients should be instructed to consult with the Investigator prior to initiating any new medication (either self-administered non-prescription drugs or prescription therapy prescribed by another physician) while participating in the study. The Investigator is expected to examine the acceptability of all

concomitant medications, topical preparations, and dietary supplements taken by patients participating in the trial.

- Medication entries should be specific to product name (if a combination drug product) and spelled correctly.
- The brand and specific product name for any over-the-counter emollient(s) should be noted and spelled correctly.
- Information on the dose, unit, frequency, route of administration, start date, discontinuation date, indication, and reason for use will be recorded.
- The use of any concomitant medication must relate to an AE listed on the AE eCRF or the patient's medical history unless it is a supplement or used as preventative care.

6.1. Permitted and Prohibited Treatments and Procedures

The use of concomitant medications for other medical conditions (e.g., hypertension, diabetes, acute infections) is permitted during this study. Inhaled corticosteroids and bronchodilators to control asthma are permitted.

The introduction of medications or therapies for other medical conditions known to affect AD (e.g., systemic corticosteroids, mycophenolate-mofetil, IFN- γ , Janus kinase inhibitors, TCI, cyclosporine, azathioprine, methotrexate, phototherapy, or photochemotherapy, phosphodiesterase-4 inhibitors such as crisaborole) are not permitted during the study. The use of systemic corticosteroids for the treatment of AD is prohibited and requires permanent discontinuation of Investigational Product. If used for treatment of AE (e.g. worsening of existing condition such as asthma exacerbation), it will still be treated as rescue medication as per Section 6.3.

Acute infections can be treated with systemic antibiotics, use of which must be recorded in the eCRF. However, chronic treatment with systemic antibiotics is not permitted.

The use of a tanning booth/parlor is not permitted during the trial.

Cannabinoid treatments for AD are prohibited.

Planned or anticipated major medical procedures or surgeries should be avoided during the trial.

See Section 6.3 for details on approved rescue medications and timing of use.

6.2. Moisturizers

Non-medicated moisturizers are to be used during the study. The patient may continue her/his current over-the-counter moisturizer regimen, if approved by the Investigator.

6.3. Rescue Treatment for Atopic Dermatitis

Induction Period

The use of topical or systemic treatments for atopic dermatitis is prohibited from Baseline through Week 16 in this study. Patients who experience intolerable AD symptoms and require treatment should, preferably, be started on topical treatments (e.g., mid-potency TCS) prior to instituting systemic treatments for AD symptoms, in accordance with best practice.

If systemic rescue treatments (e.g., oral corticosteroids, phototherapy, cyclosporin, etc.) are required, study drug must be discontinued. The patient should continue to attend all study visits through Week 16 and be assessed for safety and efficacy according to the schedule of events.

Patients requiring topical or systemic rescue medication who complete the study through Week 16 will be eligible to continue to the Escape Arm after the Week 16 visit has been completed. Patients who required systemic rescue medication must wait for rescue medication washout (≥ 5 half-lives of the medication) prior to entering the Escape Arm.

Maintenance Period

Intermittent use of topical rescue medications for AD is permitted during the Maintenance Period. Patients who may require short-term systemic treatment for symptoms of AD during the Maintenance Period will be assessed on a case by case basis and must be discussed with the Medical Monitor prior to initiating treatment.

Escape Arm

Intermittent use of topical rescue medications for AD is permitted for patients who are in the Escape Arm. Patients who may require short-term systemic treatment for symptoms of AD during the Escape Arm will be assessed on a case by case basis and must be discussed with the Medical Monitor prior to initiating treatment. Patients requiring long-term systemic treatment for symptoms of AD in the Escape Arm (e.g., non-responders) must be discontinued from the study.

The Sponsor may supply the study sites with a mid-potency and a low-potency TCS that can be provided to patients for use, if needed (e.g., triamcinolone acetonide 0.1% cream and hydrocortisone 1% cream).

All topical and systemic treatments for AD must be captured in the eCRF.

7. STUDY PROCEDURES

The required procedures for each study visit are outlined in [Appendix 1](#). The timing of each study day is relative to the day of initial dosing (Day 1, Baseline).

7.1. Screening Visit

The purpose of the screening visit/period is to ensure that appropriate patients are entered into the study and that they remain stable during the pre-treatment period.

- Obtain written informed consent/assent prior to performing any study procedures
- Review Inclusion/Exclusion Criteria
- Complete medical history/review of systems
- Review immunization record for adolescent patients
- Collect demographic information
- Measure vital signs
- Perform a complete physical examination, including height and weight

- Collect concomitant medication and procedure/therapy information
- Complete the following assessments: Investigator's Global Assessment (IGA), Body Surface Area (BSA), and Eczema Area and Severity Index (EASI)
- Draw blood samples for laboratory tests, including serum pregnancy
- Collect urine sample for urinalysis
- Assign eDiary and instruct the patient on the completion of the following assessments: Pruritus and Sleep-Loss (daily), and POEM (weekly)
- Instruct the patient to apply a moisturizer at least twice daily

7.2. **Baseline Visit (Day 1) Induction Period**

- Administer the DLQI/CDLQI and EQ-5D
- Administer the PROMIS (Patient-Reported Outcomes Measurement Information System): Anxiety and Depression measures
- Collect the ACQ-5 assessment for patients with comorbid asthma
- Update medical history/review of systems and concomitant medication and procedure/therapy information
- Complete the following assessments: IGA, BSA, EASI and SCORAD
- Review compliance report on the eDiary and confirm moisturizer use
- Measure vital signs
- Draw a pre-dose blood sample for PK and anti-drug antibody (ADA) testing
- Conduct urine pregnancy test (WOCBP only)
- Re-assess and confirm patient eligibility (Inclusion/Exclusion criteria)
- Randomize the patient, receive kit assignment, and administer study drug
- Remind patient to record the following: Pruritus and Sleep-Loss (daily), and POEM (weekly)

Sites collecting photos will also:

- Obtain written informed consent for collecting photos
- Select a target lesion and obtain a photograph

7.3. **Week 2 (\pm 3 Days)**

- Complete the following assessments: IGA, BSA and EASI
- Review and record AEs and update concomitant medication and procedure/therapy information
- Review compliance report on the eDiary, confirm moisturizer use and remind patient to record the following: Pruritus and Sleep-Loss (daily), and POEM (weekly)

- Measure vital signs
- Administer study drug

Sites collecting photos will also:

- Obtain photographs of the target lesion

7.4. Week 4 (\pm 3 Days)

- Administer the DLQI/CDLQI
- Complete the following assessments: IGA, BSA and EASI
- Review and record AEs and update concomitant medication and procedure/therapy information
- Measure vital signs
- Draw a pre-dose blood sample for PK and ADA testing
- Conduct urine pregnancy test (WOCBP only)
- Administer study drug
- Review compliance report on the eDiary, confirm moisturizer use and remind patient to record the following: Pruritus and Sleep-Loss (daily), and POEM (weekly)

7.5. Week 6 (\pm 3 Days)

- Complete the following assessments: IGA, BSA, and EASI
- Review and record AEs and update concomitant medication and procedure/therapy information
- Review compliance report on the eDiary, confirm moisturizer use and remind patient to record the following: Pruritus and Sleep-Loss (daily), and POEM (weekly)
- Measure vital signs
- Administer study drug

7.6. Week 8 (\pm 3 Days)

- Administer the DLQI/CDLQI
- Complete the following assessments: IGA, BSA and EASI
- Review and record AEs and update concomitant medication and procedure/therapy information
- Review compliance report on the eDiary, confirm moisturizer use and remind patient to record the following: Pruritus and Sleep-Loss (daily), and POEM (weekly)
- Measure vital signs
- Draw blood samples for laboratory tests, except hormones

- Collect a urine sample for urinalysis
- Conduct urine pregnancy test (WOCBP only)
- Administer study drug

Sites collecting photos will also:

- Obtain photographs of the target lesion

7.7. Week 10 (± 3 Days)

- Complete the following assessments: IGA, BSA, EASI
- Review and record AEs and update concomitant medication and procedure/therapy information
- Review compliance report on the eDiary, confirm moisturizer use and remind patient to record the following: Pruritus and Sleep-Loss (daily), and POEM (weekly)
- Measure vital signs
- Administer study drug

7.8. Week 12 (± 3 Days)

- Administer the DLQI/CDLQI
- Complete the following assessments: IGA, BSA and EASI
- Review and record AEs and update concomitant medication and procedure/therapy information
- Review compliance report on the eDiary, confirm moisturizer use and remind patient to record the following: Pruritus and Sleep-Loss (daily), and POEM (weekly)
- Measure vital signs
- Conduct urine pregnancy test (WOCBP only)
- Administer study drug

7.9. Week 14 (± 3 Days)

- Complete the following assessments: IGA, BSA and EASI
- Review and record AEs and update concomitant medication and procedure/therapy information
- Review compliance report on the eDiary, confirm moisturizer use and remind patient to record the following: Pruritus and Sleep-Loss (daily), and POEM (weekly)
- Measure vital signs
- Administer study drug

7.10. Week 16 (\pm 3 Days) Transition to Maintenance Period

- Administer the DLQI/CDLQI, and EQ-5D
- Administer the PROMIS measures
- Collect ACQ-5 for patients with comorbid asthma
- Complete the following assessments: IGA, BSA, EASI and SCORAD
- Perform a complete physical examination, including height and weight
- Review and record AEs and update concomitant medication and procedure/therapy information
- Review compliance report on the eDiary, confirm moisturizer use and remind patient to record the following: Pruritus and Sleep-Loss (daily), and POEM (weekly)
- Measure vital signs
- Draw pre-dose blood samples for laboratory tests, PK and ADA testing
- Collect a urine sample for urinalysis
- Conduct urine pregnancy test (WOCBP only)
- Re-randomize the patient to the Maintenance Period
- Train the patient to self-administer study drug
- Administer one injection and observe the patient self-injecting
- Dispense study drug for Week 18 injections

Sites collecting photos will also:

- Obtain a photograph of the target lesion

7.11. Week 20 (\pm 5 Days)

- Complete the following assessments: IGA, BSA and EASI
- Review and record AEs and update concomitant medication and procedure/therapy information
- Review compliance report on the eDiary, confirm moisturizer use and remind patient to record the following: Pruritus and Sleep-Loss (daily), and POEM (weekly)
- Measure vital signs
- Conduct urine pregnancy test (WOCBP only)
- Administer or observe the patient self-injecting study drug
- Dispense study drug for Week 22 injection
- Remind the patient to apply moisturizer and to complete the eDiary as instructed

7.12. Week 24 (± 5 Days)

- Complete the following assessments: IGA, BSA and EASI
- Review and record AEs and update concomitant medication and procedure/therapy information
- Review compliance report on the eDiary, confirm moisturizer use and remind patient to record the following: Pruritus and Sleep-Loss (daily), and POEM (weekly)
- Measure vital signs
- Conduct urine pregnancy test (WOCBP only)
- Administer or observe the patient self-injecting study drug
- Dispense study drug for Week 26 injection
- Remind the patient to apply moisturizer and to complete the eDiary as instructed

7.13. Week 28 (± 5 Days)

- Complete the following assessments: IGA, BSA and EASI
- Review and record AEs and update concomitant medication and procedure/therapy information
- Review compliance report on the eDiary, confirm moisturizer use and remind patient to record the following: Pruritus and Sleep-Loss (daily), and POEM (weekly)
- Measure vital signs
- Conduct urine pregnancy test (WOCBP only)
- Administer or observe the patient self-injecting study drug
- Dispense study drug for Week 30 injection
- Remind the patient to apply moisturizer and to complete the eDiary as instructed

7.14. Week 32 (± 5 Days)

- Administer the DLQI/CDLQI
- Complete the following assessments: IGA, BSA and EASI
- Perform a complete physical examination, including height and weight
- Review and record AEs and update concomitant medication and procedure/therapy information
- Review compliance report on the eDiary, confirm moisturizer use and remind patient to record the following: Pruritus and Sleep-Loss (daily), and POEM (weekly)
- Measure vital signs
- Draw blood samples for laboratory tests, PK and ADA testing

- Collect a urine sample for urinalysis
- Conduct urine pregnancy test (WOCBP only)
- Administer or observe the patient self-injecting study drug
- Dispense study drug for Week 34 injection
- Remind the patient to apply moisturizer and to complete the eDiary as instructed

7.15. Week 36 (± 5 Days)

- Complete the following assessments: IGA, EASI, and BSA
- Review and record AEs and update concomitant medication and procedure/therapy information
- Review compliance report on the eDiary, confirm moisturizer use and remind patient to record the following: Pruritus and Sleep-Loss (daily), and POEM (weekly)
- Measure vital signs
- Conduct urine pregnancy test (WOCBP only)
- Administer or observe the patient self-injecting study drug
- Dispense study drug for Week 38 injection
- Remind the patient to apply moisturizer and to complete the eDiary as instructed

7.16. Week 40 (± 5 Days)

- Complete the following assessments: IGA, BSA and EASI
- Review and record AEs and update concomitant medication and procedure/therapy information
- Review compliance report on the eDiary, confirm moisturizer use and remind patient to record the following: Pruritus and Sleep-Loss (daily), and POEM (weekly)
- Measure vital signs
- Conduct urine pregnancy test (WOCBP only)
- Administer or observe the patient self-injecting study drug
- Dispense study drug for Week 42 injection
- Remind the patient to apply moisturizer and to complete the eDiary as instructed

7.17. Week 44 (± 5 Days)

- Complete the following assessments: IGA, EASI, and BSA
- Review and record AEs and update concomitant medication and procedure/therapy information

- Review compliance report on the eDiary, confirm moisturizer use and remind patient to record the following: Pruritus and Sleep-Loss (daily), and POEM (weekly)
- Measure vital signs
- Conduct urine pregnancy test (WOCBP only)
- Administer or observe the patient self-injecting study drug
- Dispense study drug for Week 46 injection
- Remind the patient to apply moisturizer and to complete the eDiary as instructed

7.18. Week 48 (± 5 Days)

- Complete the following assessments: IGA, BSA and EASI
- Review and record AEs and update concomitant medication and procedure/therapy information
- Review compliance report on the eDiary, confirm moisturizer use and remind patient to record the following: Pruritus and Sleep-Loss (daily), and POEM (weekly)
- Measure vital signs
- Conduct urine pregnancy test (WOCBP only)
- Administer or observe the patient self-injecting study drug
- Dispense study drug for Week 50 injection
- Remind the patient to apply moisturizer and to complete the eDiary as instructed

7.19. Week 52 (± 5 Days) End of Study

- Administer the DLQI/CDLQI, and EQ-5D
- Administer the PROMIS measures
- If the patient has reported a history of asthma, collect the ACQ-5 assessment
- Complete the following assessments: IGA, BSA, EASI and SCORAD
- Perform a complete physical examination, including height and weight
- Review and record AEs and update concomitant medication and procedure/therapy information
- Review compliance report on the eDiary and collect eDiary
- Measure vital signs
- Draw blood samples for laboratory tests, PK and ADA testing
- Collect a urine sample for urinalysis
- Conduct urine pregnancy test (WOCBP only)

7.20. Early-Termination Visit

Patients who discontinue the study early for any reason should have these assessments performed at their early-termination visit. The reason for early termination must be recorded in the eCRF (see Section 8.7.1).

- Administer the DLQI/CDLQI, and EQ5D
- Administer the PROMIS measures
- Collect the ACQ-5 assessment for patients with comorbid asthma
- Complete the following assessments: IGA, BSA, EASI and SCORAD
- Perform a complete physical examination, including height and weight.
- Review and record AEs and update concomitant medication and procedure/therapy information
- Review compliance report on the eDiary and collect eDiary
- Measure vital signs
- Draw blood samples for laboratory tests, PK and ADA testing
- Collect a urine sample for urinalysis
- Conduct urine pregnancy test (WOCBP only)

If the Early Termination Visit is during the Induction Period, sites collecting photos will also:

- Obtain a photograph of the target lesion

7.21. Safety Follow-up Visit

Patients who terminate early from the study or do not enroll in the long-term extension study, DRM06-AD07, will undergo a follow up visit approximately 12 weeks after the last study drug injection.

- Update AEs and concomitant medications and procedures that were ongoing at study termination
- Draw blood samples for PK and ADA testing.

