
Investigator's Signature

Date

Investigator's Name (print)

PROTOCOL SYNOPSIS

Title:	A RANDOMIZED, DOUBLE-BLIND, PLACEBO-CONTROLLED TRIAL TO EVALUATE THE EFFICACY AND SAFETY OF LEBRIKIZUMAB IN PATIENTS WITH MODERATE-TO-SEVERE ATOPIC DERMATITIS
Protocol Number:	DRM06-AD05
Phase:	3
Number of Sites:	Approximately 100 sites in the United States (US), European Union (EU) and Asia/Pacific region.
Study Population:	
Adolescent patients (≥ 12 to < 18 years weighing ≥ 40 kg) and adults with moderate-to-severe atopic dermatitis (AD) who are candidates for systemic therapy.	
Sample Size:	
Approximately 400 patients with moderate-to-severe AD, including approximately 50 adolescent patients.	
Study Objectives:	
To evaluate the safety and efficacy of lebrikizumab compared with placebo in patients with moderate-to-severe AD.	
Duration of Patient Participation:	
Screening: Maximum duration of 30 days	
Induction Period: 16 weeks	
Maintenance Period: 36 weeks	
Safety Follow Up: 12 weeks	
Maximum total participation: 66 weeks	
For patients terminating early or not rolling into the long-term extension study (LTE), a safety follow-up visit will occur 12 weeks after last dose of study medication.	
Completion of Patient Participation: A patient is considered to have completed the study if he/she has completed the last scheduled visit:	

 • For subjects continuing into LTE, upon completion of week 52 visit and rolling into LTE study 	

- For subjects not continuing into LTE, when subject had either week 52 or Early Termination Visit (ETV), and safety follow up visit (12 weeks after last IP administration)

Study Treatment:

Lebrikizumab, 250 mg (2 mL injection of 125 mg/mL)

Placebo, 2 mL injection.

Study Design:

This is a randomized, double-blind, placebo-controlled, parallel-group study which is 52 weeks in duration. The study is designed to confirm the safety and efficacy of lebrikizumab as monotherapy for moderate-to-severe atopic dermatitis utilizing a 16-week induction treatment period and a 36-week long-term maintenance treatment period.

Eligible adult and adolescent (≥ 12 to < 18 years weighing ≥ 40 kg) patients with moderate-to-severe atopic dermatitis for at least one year, defined according to the American Academy of Dermatology Consensus Criteria, an Eczema Area and Severity Index Score (EASI) of ≥ 16 , an Investigator Global Assessment (IGA) score of ≥ 3 and a body surface area (BSA) of $\geq 10\%$ will be enrolled.

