Serum samples will be collected for pharmacokinetic analysis and immunogenicity.

Photographs of a selected target lesion will be obtained in a subset of patients participating in this study.

Patients completing this 52-week study will be offered the option of continued treatment in a separate long-term extension study (DRM06-AD07).

[figure not shown]
Patients who early terminate or choose not to enter the long-term extension study will undergo a follow-up visit approximately 12 weeks after the last study drug injection for safety follow-up.

A patient is considered to have completed the study if he/she has completed the last scheduled visit:

- For subjects continuing into LTE, upon completion of week 52 visit and rolling into LTE study
- For subjects not continuing into LTE, when subject had either week 52 or ETV, and safety follow up visit (12 weeks after last IP administration)

The end of the study is defined as the date of the last visit of the last patient in the study shown in the Schedule of Visits and Procedures.

Figure 1: Study Schema

* Responder is defined as having an IGA of 0 or 1 or a 75% reduction in EASI from Baseline to Week 16 (EASI-75)

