3.1. Duration of the Study

The total duration of a patient's participation in this study will be approximately 66 weeks (Screening: maximum duration of 30 days; Induction Period: 16 weeks; Maintenance Period: 36 weeks; Follow Up: 12 weeks from last dose at Week 50).

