8.5.4. Adverse Events

Adverse events will be monitored throughout the study. Patients will be instructed to inform the Investigator and/or study staff of any AEs. At each visit, patients will be asked about AEs in a non-specific manner using open-ended questions so as not to bias the response (e.g., How have you been since the last visit?). Specific inquiry regarding reported AEs will be conducted when applicable. All AEs will be documented and recorded in the patient's eCRF.

Any patient who has an AE (serious or non-serious) will be evaluated by the Investigator and treated and followed until the symptom(s) return to normal or to clinically acceptable levels, as judged by the Investigator. A physician, either at the clinical site, or at a nearby hospital

emergency room, will administer treatment for any serious AEs (SAEs), if necessary. When appropriate, medical tests and examinations will be performed to document resolution of event(s).

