8.5.4.4. Reporting of SAEs

All SAEs, as defined in Section 8.5.4.3, regardless of causal relationship, must be reported to the Sponsor or designee within 24 hours of the Investigator becoming aware of the event. As soon as the Investigator becomes aware of an AE that meets the criteria for an SAE, the SAE should be documented to the extent that information is available.

SAEs will be recorded from the time of informed consent/assent until the end of the study. If, in the opinion of the Investigator, an SAE occurring outside the specified time window (i.e., following patient completion or terminations of the study) is deemed to be drug-related, the event should be reported with 24 hours.

SAEs must be recorded on study-specific SAE forms which will be provided to the site. The minimum information required for SAE reporting includes the identity of the PI, site number, patient number, event description, SAE term(s), reason why the event is considered serious (i.e., the seriousness criteria), and PI's assessment of the relationship of the event to study drug. Additional SAE information including medications or other therapeutic measures used to treat the event, and the outcome/resolution of the event should also be recorded on the SAE form.

In all cases, the Investigator should continue to monitor the clinical situation and report all material facts relating to the progression or outcome of the SAE. The Investigator may be required to provide supplementary information as requested by the Sponsor or its designee.

When reporting SAEs, the following additional points should be considered:

- Although signs, symptoms, and tests that support the diagnosis of an SAE should be provided, the Investigator should report the diagnosis or syndrome as the SAE term.
- Death should not be reported as an SAE, but as an outcome of a specific SAE (unless the event preceding the death is unknown). If an autopsy was performed, the autopsy report should be provided.

Although most hospitalizations necessitate reporting of an SAE, some hospitalizations do not:

- Hospitalization for elective or previously scheduled surgery, or for a procedure for a pre-existing condition that has not worsened after administration of study drug (e.g., a previously scheduled ventral hernia repair). SAEs must, however, be reported for any surgical or procedural complication that lead to prolongation of the hospitalization.

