6.1.4. General Considerations for Safety Analyses for Combined Induction and Maintenance Periods

Adverse event, exposure summary, and categorical laboratory/vital sign changes will be provided for the All Lebrikizumab Modified Safety Population and the All Lebrikizumab Safety Population during the Combined Induction and Maintenance Periods. For patients who were first exposed to lebrikizumab during Induction Period, the baseline for TEAE will utilize the baseline for Induction Period defined in Section 6.1.2; for patients who were first exposed to lebrikizumab during Maintenance Period, the baseline for TEAE will utilize the baseline for Maintenance Period defined in Section 6.1.3.

More details on baseline and postbaseline definitions can be found in the Compound Level Safety Standard.

6.1.5. General Considerations for Safety Analyses for Combined Induction and Maintenance Periods Plus Follow Up Period

Selective AE summaries will be provided for the All Lebrikizumab Modified Safety Population and the All Lebrikizumab Safety Population during the Combined Induction and Maintenance Periods plus Follow up Period. The baseline definition for this population is the same as Section 6.1.4. More details on baseline and postbaseline definitions can be found in the Compound Level Safety Standard.

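### Protocol 7.21 words the follow-up AE task more narrowly than the rest of the plan, so new events between Week 52 or early termination and follow-up may go unrecorded; the SAE window wording is also ambiguous

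*Protocol*

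**What the plan says.** **The follow-up visit.** Patients who stop early or do not enter the extension study "will undergo a follow up visit approximately 12 weeks after the last study drug injection" (Protocol 7.21). The AE task there is to "Update AEs and concomitant medications and procedures that were ongoing at study termination". PK and ADA samples are drawn at the same visit.

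**The other AE rules.** Protocol 8.5.4 states: "Adverse events will be monitored throughout the study". It adds that patients are asked an open question about AEs at each visit. Section 8.5.4.1 has every AE during the study entered individually in the eCRF. Table 7 marks Adverse Events at Safety F/U, with no footnote limiting the entry to ongoing events.

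**SAEs.** Protocol 8.5.4.4 requires all SAEs, whatever the causality, from consent or assent to the end of the study. It then adds a rule for the case where "an SAE occurring outside the specified time window (i.e., following patient completion or terminations of the study) is deemed to be drug-related". Section 3 defines completion as: "For subjects not continuing into LTE, when subject had either week 52 or ETV, and safety follow up visit (12 weeks after last IP administration". It defines the end of the study as the last patient's last visit.

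**The analysis.** SAP 6.1.5, on the combined periods plus follow-up, says: "Selective AE summaries will be provided for the All Lebrikizumab Modified Safety Population and the All Lebrikizumab Safety Population". SAP 6.14.1 includes any follow-up period in the exposure calculated for that analysis.

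**The concern.** An AE that begins after the Week 52 or early-termination visit was not ongoing at termination, so on its natural reading the 7.21 bullet does not cover it. The visit-by-visit sections serve as the site's checklist, and sites could therefore collect differently depending on whether they work from 7.21 or from 8.5.4 and Table 7.

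The patients concerned are those who left early, some of them because of an AE, and those who declined the extension. The SAP adds their follow-up time to exposure and summarises their AEs over it. If time is added but new events are not, late AEs are understated, and the ADA result from that visit has no matching record of new events.

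The SAE text raises a second, separate question: at what point, for an individual patient, does reporting regardless of causality stop?

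**Working it through.** **1. Reproduce the plan's own duration.** The synopsis gives "Maximum total participation: 66 weeks" and Protocol 3.1 gives "Follow Up: 12 weeks from last dose at Week 50". Screening is at most 30 days.

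- From last dose: 30/7 + 50 + 12 = 4.29 + 50 + 12 = 66.29 weeks, which agrees with 66.
- From Week 52 instead: 4.29 + 52 + 12 = 68.29 weeks, which does not.

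Follow-up is therefore at about Week 50 + 12 = 62, and the protocol counts it as part of participation.

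**2. Interval at risk for a completer.** The Week 52 visit (7.19) still records all AEs, so the interval starts there and not at the last dose: 62 − 52 = 10 weeks, and 10/62 = 16% of the time from first dose to follow-up.

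**3. Interval at risk after early termination.** The gap is 12 − d weeks, where d is the time from last dose to the Early-Termination Visit. The protocol gives no figure for d; 8.7.1 asks for the visit as soon as possible. For a patient last dosed at Week 14 (follow-up at Week 26):

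| Assumed d (weeks) | Gap (weeks) | Share of time from first dose to follow-up |
|---|---|---|
| 0 | 12 | 12/26 = 46% |
| 2 | 10 | 10/26 = 38% |
| 4 | 8 | 8/26 = 31% |

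For a patient last dosed at Week 30 with d = 2, the share is 10/42 = 24%.

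**4. Effect on a rate, if one is computed.** Assume a constant event rate, exposure counted from first dose, and no new events recorded in the gap. An exposure-based rate is then multiplied by 1 − gap share: 52/62 = 0.84 for a completer, 16/26 = 0.62 for a last dose at Week 14 (d = 2) and 32/42 = 0.76 for Week 30 (d = 2). These are worst-case, per-patient illustrations. SAP 6.14.2 describes its AE tables as numbers and percentages of patients; in those, the effect would be missing late cases and not a rescaled rate.

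**5. Amount of time involved.** The documents give no proportion of patients who do not roll over. Assuming 15–25% of about 400, that is 60–100 patients. At 10 weeks each: 60 × 10 × 7/365.25 = 11.5 and 100 × 10 × 7/365.25 = 19.2 patient-years. Anyone never given lebrikizumab would be outside the affected summaries, so their share would be smaller.

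**6. AE texts side by side.**

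| Place | AE task |
|---|---|
| 7.3–7.19 (Week 2 to Week 52), 7.20, 7.22 | Review and record |
| 7.21 | Update, with a restriction to what was ongoing |
| 8.5.4 | Ask at each visit |
| 8.5.4.1 | Record all AEs during the study |
| Table 7, Safety F/U column | AE entry, no restriction |

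The Table 7 layout confirms that the tick is real: the AE row has ten marks (eight visits from Week 20 to Week 48, Week 52/ET, Safety F/U), whereas the vital-signs row has nine.

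**7. SAE texts side by side.** The main sentence of 8.5.4.4 runs to the end of the study, which Section 3 places at the last patient's last visit. The parenthesis that follows puts the time after a patient's completion or termination outside the window. Section 8.7.1 treats patients as terminated before their Early-Termination Visit, and 7.21 places termination before follow-up. On that usage an early terminator's whole follow-up would be outside. The heading of 7.19 also labels Week 52 as the end of the study. Against this, the Section 3 completion rule requires the follow-up visit after either Week 52 or early termination, which keeps follow-up inside. Section 8.7 also uses study termination for the sponsor stopping the trial.

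**The case against.** The strongest reply is that the plan already requires what is asked for. The word only does not appear in 7.21, and its last clause can be attached to medications and procedures alone. Sections 8.5.4, 8.5.4.1 and Table 7 set no limit at follow-up. The 48-hour rule for AEs of special interest (8.5.4.2) has no cut-off at termination, and the TEAE definition in Protocol 9.11 has no end date. This stands to the extent that the evident intention is to capture AEs through follow-up. It does not remove the conflict: the one section written for this visit is narrower than the wording at every other post-baseline visit.

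Three stronger readings are tempting, and the documents do not support them.

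- A reader might infer that new events after the last dose are lost. The Week 52 and Early-Termination visits record all AEs, and the general rules still apply afterwards. What remains is a risk of non-recording after those visits.
- A reader might infer that early terminators' SAEs are filtered by causality while completers' are not, so that SAE counts depend on how a patient left. That rests on one ambiguous parenthesis, and the Section 3 completion rule treats both groups alike.
- A reader might apply the conjunctivitis percentages quoted from earlier studies to count missed cases. Those are incidences over whole studies with active dosing, and they do not carry over to about 10 weeks off drug.

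**Conclusion.** This is an internal inconsistency that should be corrected; it is not a flaw in the trial's design. Taken literally, 7.21 leaves new non-serious AEs at risk of not being recorded for about 10 weeks in a completer and, depending on the timing of the Early-Termination Visit, roughly 8 to 12 weeks in an early terminator. How much is missed depends on how sites read the bullet and on how many patients attend the visit, and the documents settle neither.

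The consequence is confined to the summaries that add follow-up. These are selective, restricted to lebrikizumab-treated patients and without between-group comparison (SAP Table KGAC.6.2). The randomised induction and maintenance safety comparisons do not use this interval. SAP 6.1.5 leaves the detailed baseline and post-baseline definitions to a compound-level standard that is not among the documents.

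On SAEs the conclusion is narrower. The text of 8.5.4.4 can be read in two ways, and reporting regardless of causality through follow-up is at least as well supported as the restrictive reading. A site should not have to choose between them.

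**What to change.** 1. In Protocol 7.21, replace the first bullet with the AE and concomitant-medication bullet already used at Week 52 and the Early-Termination Visit (7.19, 7.20), so that new, worsened and ongoing events are all covered.
2. In 8.5.4.4, reconcile the parenthesis with Section 3: state that SAEs are reported regardless of causality through each patient's Safety Follow-up Visit, or entry into the extension study, and that the drug-related condition applies only after that.
3. If follow-up visits have already taken place under the present wording, say in the report of the summaries that include follow-up what was collected at them.

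The first two are wording changes. Blood is already drawn at this visit and an AE entry is already scheduled, so no new procedure is needed. The cost is a few more AE records and queries.
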